Older adults with impaired fasting glucose (IFG) will be randomized to into a double-blinded, placebo-controlled intervention study with metformin. This clinical trial has the primary outcome of change in appendicular lean mass and physical performance assessed between baseline and year 3 based on our prior observational findings above and Power calculations below. The secondary outcome of change in muscle histology over 6 months using muscle biopsies is planned in a substudy of participants given previous studies that show significant biological effects on muscle with metformin treatment during this time interval.^{32, 61}

Study Population

Inclusion criteria: 120 randomized, sedentary, weight-stable, ambulatory men and women 65 years or older with pre-diabetes identified with IFG (100 mg/dL \leq fasting glucose<126 mg/dL) on no diabetes medications. Participants must demonstrate that they are able to ambulate 400 meters without assistance. Participants must be able to fast for 12 hours prior to blood draw.

Subjects who meet the above inclusion criteria and meet the additional exclusion criteria for the Muscle Biopsy Substudy listed below will be considered for enrollment (32 subjects) in the muscle biopsy substudy.

Exclusion criteria: Participants will be excluded if they plan to move away from the Portland metropolitan area during the 3 year study time frame. Participants with conditions that are relative contraindications to metformin or affect muscle mass or performance measurements will be excluded as outlined below. Specific criteria are delineated below.

Exclusion Criteria

- 1. Chronic medical conditions affecting muscle mass or function
 - a. Active non-skin cancer
 - b. Hypogonadism
- 2. Medications affecting muscle mass or function See section "Prohibited Medications."
- 3. Lifestyle factors affecting muscle
 - a. Intentional/unintentional weight loss
 - b. Vigorous regular exercise
- 4. Contraindications to metformin
 - a. Renal dysfunction defined as creatinine $\geq 1.5~mg/dL$ for men or $\geq 1.4~mg/dL$ for women or eGFR< 60 mL/min
 - b. Liver dysfunction defined as ALT > 48 U/L, AST > 41 U/L
 - c. B12 deficiency defined as B12 level < 180 pg/mL
 - d. Congestive heart failure
 - e. Known hypersensitivity to metformin
 - f. Excessive alcohol intake (average of ≥ 2 alcoholic beverages/day over a month)
 - g. Serious medical condition in the opinion of the investigator

Additional Exclusion Criteria for Muscle Biopsy Substudy

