Initial contact with potential subjects will occur in clinic, by phone or by mail. If in clinic, their provider will approach them first to see if they are interested in the study and ask if they agree to be contacted by study personnel. If the patient agrees, they can initiate contact with the study team by phone or have the study coordinator speak to them in clinic or call them later. If initial contact is by phone, potential subjects can contact the study coordinator directly using information on the advertising flyers. If initial contact is by mail, potential subjects will receive a recruitment letter indicating the option to opt out by returning an included letter indicating the wish to not be contacted again. The letter will state that if a response is not received within two weeks, potential subjects may be contacted by phone. Included with this mailing will be an approved informational letter from the Chief of Primary Care.

During the screening telephone call, a study coordinator will discuss the inclusion and exclusion criteria and provide further details on the study. If participants are interested and are potentially eligible, a Screening visit will be scheduled.

Study design

The proposed study duration of 3 years has been selected based on our prior observational findings over 3.5 years.²⁵ Eligible participants will have an initial Baseline visit, followed by randomization to placebo or metformin (Fig. 7). Between visits, telephone surveying of medication compliance will be obtained and any AEs reviewed. Participants will be seen every 6 months, and have annual study visits for measurements of muscle mass and performance. A substudy of participants will also include muscle biopsies at 2 visits; within 14 days from baseline and at the 6 month visit.

9

Primary outcome measures

To test the primary hypothesis that metformin-treated participants will have a slower decline in muscle mass and physical performance than those on placebo, we will be measuring total and appendicular lean mass using dual x-ray absorptiometry and assessing physical performance with the short physical performance battery (SPPB), grip strength and a 400 meter walk. Our preliminary findings suggest that there should be attenuation in the loss in appendicular lean mass and gait speed, and additional performance measures will be explored.

Secondary outcome measures

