progress to diabetes yearly,^{72, 79, 80} all efforts will be made to retain these participants in the study and to include them in intent-to-treat analyses. The Power and effect size estimates for gait speed (SD=0.19) for α =0.05 for 60 participants and 53 participants per group are illustrated in the graph (Fig. 8) and based on our preliminary data in older women. The sample size of 60 participants per group will have 73% Power to detect a 0.09 m/s difference in gait speed. Within each group, 16 participants will be randomly selected and consented to undergo muscle biopsies at baseline and 6 months for secondary analyses of muscle histologic changes with metformin vs. placebo treatment. There is an expected change in these histologic measures within 6 months given prior studies that detect changes in AMPK activation, ATP concentration and insulin sensitivity prior to 6 months with use of metformin.^{3, 4} Estimated effect sizes of the difference in histologic measures between the two groups after 6 months are shown below in Table 3. While this study is adequately powered for 3 year outcomes in muscle loss, interim analyses may be performed by a Data Monitoring Committee (managed by the VA CSRD), given blinding of the primary investigator to the intervention, and the trial may be terminated early if a significant difference in the primary outcome between metformin- and placebo-treated groups is noted before 3 years.

	SD	70%	80%	90%
Capillary Density (AU)	0.35	0.32	0.36	0.42
IMCL (AU)	0.50	0.46	0.51	0.59
SDH (AU)	0.50	0.46	0.51	0.59
% Type I Fibers	24.0	21.8	24.6	28.4

Table 3 Estimated detectable difference in muscle histology measures at 80 and 90% Power

SD derived from measures in older insulin-resistant adults³⁶

Statistical Analyses

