To assess a difference in the primary outcomes of change in muscle mass and performance between metforminand placebo-treated groups, longitudinal (mixed effects) models will be used to estimate the trajectory of change. These models will account for correlation of outcomes within subjects and allows for those with missing followup data to be included in analyses. Four measures of muscle mass and performance (baseline, year 1, 2 and 3) are the outcomes in separate models. These will be modeled as a linear change over time, and other functional changes (squared, cubic and quadratic) will be evaluated. In the best fitting model, an interaction between time and group (metformin vs. placebo) will be included in the model to determine if changes in muscle mass/performance differ between the two groups. For the secondary outcomes of muscle histology, the discrete change in measures of mitochondrial content, muscle capillary density, percentage of fiber types and intramyocellular lipid content over 6 months will be calculated. The absolute and percentage changes in these measures will serve as the outcome in linear regression models with treatment group as the dichotomous exposure. Nonlinear associations between the exposure and outcomes will be evaluated with higher order terms. For the analyses of primary and secondary outcomes, potential confounders including demographic information, physical activity, diet, lifestyle factors, medical history and medication use are expected to be evenly distributed between the groups in a random fashion; nevertheless, we will evaluate for potential confounding by these factors and include them in multivariable models if they are significantly associated with our exposure and outcome and modify the effect size by >10%. There is no anticipated gender difference in the study outcomes, so the study has not been powered to detect a significant interaction by gender. However, the primary and secondary outcomes will also be stratified by gender to explore if there is a gender-specific muscle response to metformin. To account for missing data, multiple imputation modeling will constructed from participants with complete data. Participants with missing data will have those values imputed at each time point multiple imputation.⁸² Results will be reported with and without imputed values.

Data Integrity

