Potential benefits to participants include the detection and potentially earlier treatment of diabetes mellitus. Participants in both metformin and placebo groups will benefit from routine lifestyle modification counseling at yearly visits for prevention of diabetes.

Others may benefit from a greater understanding of the effect of metformin on muscle mass and function in insulin-resistant older adults.

VA Data Monitoring Committee (DMC)

A data monitoring committee will be provided by VA CSR&D. With DMC's experience in the conduct and monitoring of clinical trials, it will assist with ensuring the overall safety of study participants, assessing safety and efficacy of the study intervention, monitoring the overall conduct of the clinical trial including recommendations on recruitment and retention of participants and improvement of study drug adherence, and providing recommendations on stopping or continuation of the trial. SAEs and UPRs will be reported to the DMC. For further details, see the "Instructions for the Review of New (uninitiated) Protocols by DMC Members."

Inclusion of Women and Children

Because sarcopenia is a condition of older age, children will not be enrolled in this study. Women will be included in a proportion reflective of their gender distribution at the VAPORHCS.

Criteria for Discontinuation

Subjects will be withdrawn from further study drug administration in the event of any of the following:

• Diagnosis of diabetes

- If hospitalized for any reason and after 48 hours of discharge, there is evidence of renal dysfunction
- If they require contrast medium and after 48 hours of procedure, there is evidence of renal dysfunction
- Developed lactic acidosis
- Developed renal insufficiency at the level indicated by the FDA ($eGFR < 45 \text{ mL/min}/1.73 \text{ m}^2$).
- Development of B12 deficiency
- Excessive alcohol intake
- Subject withdraws consent
- Significant deviation from the protocol or eligibility criteria in the opinion of the investigator
- Any other reason that in the opinion of the investigator, would justify removing the subject from the study

There are no pre-defined stopping rules for termination of the study.

VA Research:

The following are the components of the study which will be conducted at the VAPORHCS:

- Advertising
- Recruitment
- Study visit activities at Screening, Baseline, half-yearly visits, and annual visits
 - Consent
 - Height, weight
 - o Blood pressure
 - Demographics
 - Medical history

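### The trial may stop early on a significant difference, but no look schedule, interim boundary or final alpha is stated; if 0.05 is reused, the false-positive risk exceeds 5%

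*Combined protocol and SAP*

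**What the plan says.** All references are to the combined protocol and SAP.

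- **Sample Size and Power.** The trial is sized on percentage change in appendicular lean mass: difference 2.2%, SD 4%, two-sided alpha 0.05, unpaired t-test, 80% power, 106 participants (53 per group). It randomizes 120, allowing for 7.5-10% dropout. Gait speed power is also given at alpha 0.05. The DMC may perform interim analyses, and "the trial may be terminated early if a significant difference in the primary outcome between metformin- and placebo-treated groups is noted before 3 years".
- **Statistical Analyses.** "Four measures of muscle mass and performance (baseline, year 1, 2 and 3) are the outcomes in separate models". This section mentions no interim look and gives no alpha.
- **VA Data Monitoring Committee.** The committee's remit includes assessing efficacy as well as safety, and "providing recommendations on stopping or continuation of the trial". For details it points to a separate document, "Instructions for the Review of New (uninitiated) Protocols by DMC Members".
- **Criteria for Discontinuation.** The section ends: "There are no pre-defined stopping rules for termination of the study".
- **Overview and Primary outcome measures.** "This clinical trial has the primary outcome of change in appendicular lean mass and physical performance assessed between baseline and year 3". The performance side means "assessing physical performance with the short physical performance battery (SPPB), grip strength and a 400 meter walk".

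**The concern.** The sentence on early termination is an efficacy stopping criterion with its threshold left open. A committee applying it would have only one number in the protocol to turn to, the planning alpha of 0.05. Testing repeatedly at 0.05 and acting on the first crossing gives more than a 5% chance of a false positive, while the sample size assumes a single test at 5%.

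The protocol also does not tell the committee which difference counts, because *the primary outcome* covers lean mass and several performance tests. The discontinuation section then says no stopping rule exists.

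An early stop on this basis would give up the planned 3-year comparison and would tend to exaggerate the effect. The Summary of the preliminary studies presents the randomized trial as the necessary check on the observational findings, so a loose error rate weakens the trial's main purpose.

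**Working it through.** **1. The plan's own figure.** Inputs from Sample Size and Power: d = 2.2, SD = 4, two-sided alpha 0.05, power 80%.

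n per group = 2(1.960 + 0.842)² × 4² / 2.2² = 51.9 by the normal approximation. The exact t-test gives 79.3% power at 52 per group and 80.1% at 53. The stated 53 per group (106) is therefore reproduced as a fixed design with one test. It contains no allowance for interim looks.

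**2. False-positive risk if 0.05 is reused.** The risk is P(|Z_k| > 1.96 at any analysis) under no effect, where the Z_k are jointly normal with corr(Z_i, Z_j) = √(t_i/t_j) and t is the information fraction. The protocol gives no fractions, so these are assumptions.

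One look plus final:

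| t | Risk |
|---|---|
| 0.10 | 9.5% |
| 0.50 | 8.3% |
| 0.88 | 6.6% |

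For looks after the year 1 and year 2 visits I used the information on a linear slope. With visits at years 0, 1, 2 and 3, the sums of squares of time to years 1, 2 and 3 are 0.5, 2 and 5. The slope variance with data to year m is σ_b² + σ_e²/SS_m, with 9σ_b² + 2σ_e² = 4² = 16 (the variance of 3-year change). Let f = 9σ_b²/16 be the share of that variance due to true differences in slope. The protocol does not give f. For f = 0.5, σ_b² = 0.889 and σ_e² = 4. The variances are then 8.889, 2.889 and 1.689, so t = 1.689/8.889 = 0.19 and 1.689/2.889 = 0.585.

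| Look fractions | Basis | Risk, two looks plus final |
|---|---|---|
| 0.10, 0.40 | f = 0 | 12.5% |
| 0.19, 0.585 | f = 0.5 | 11.6% |
| 1/3, 2/3 | equal steps | 10.7% |
| 0.325, 0.743 | f = 0.75 | 10.6% |
| 0.55, 0.88 | f = 0.9 | 9.2% |
| 0.90, 0.98 | f about 0.985 | 6.8% |

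The excess shrinks as the interim data come to determine the final result. In the most extreme case tried (an ordinary slope estimate with between-person slope variance 100 times the error variance) the risk is 5.7%. It was above 5% in every case.

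**3. The proposed boundary.** Two-sided p<0.001 at each interim is |Z| > 3.29.

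- Final p<0.048: 0.001 + 0.001 + 0.048 = 0.050, so the overall level cannot exceed 5% at any timing if each test has its nominal size. By integration it is 4.8% to 4.9% over the fractions above. The required information rises by a factor of 1.011 to 1.012, or 106 × 1.012 = 107.3 completers.
- Final p<0.0488: overall 4.9% to 5.0%, factor 1.006 to 1.007, or 106 × 1.007 = 106.7 completers.
- O'Brien-Fleming-type spending, 0.025 per tail: 107.4 completers at equal steps (z = 3.71, 2.51, 1.99), 107.9 at 0.325/0.743 and 108.8 at 0.55/0.88.

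Expected completers are 120 × 0.90 = 108 to 120 × 0.925 = 111.

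**The case against.** The strongest reply is that nothing here is bound to happen. Interim analyses are optional, termination is optional, and the committee only recommends. This stands in part. The percentages above are upper values for their look patterns, because they assume that every crossing stops the trial or is declared positive. It does not remove the point, because the protocol authorizes the look, names the trigger and fixes no level before data are seen.

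A second reply is that the committee may hold a boundary in its own instructions. That cannot be excluded, since the document was not available. Its title concerns the review of new protocols, so whether it contains a boundary is unknown. If it does, the repair is to state it in the protocol.

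Third, the Potential Risks section says the study is not meant to support a significant labeling change. That limits the harm to the reliability of the trial's own conclusion.

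A reader might infer that the trial's error rate *is* 8% to 12%, or that no boundary exists anywhere. The documents support neither reading. They show only that the protocol is silent and that the one alpha it gives would not hold 5% if reused. A reader might also add inflation from testing several performance measures. That is a separate multiplicity question, and the figures here are per outcome.

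**Conclusion.** The point holds in conditional form. The protocol states an efficacy stopping criterion without a schedule, boundary or final alpha, and its two statements on stopping need to be reconciled. That much is plain from the text.

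The size is less certain. It depends on three conditions: an efficacy look takes place, 0.05 is reused, and a crossing is acted on. It also depends on assumed information fractions. Under those conditions the risk is about 8.3% for one look at half information and 10.7% for two equally spaced looks. The range for two looks is about 7% when information is very advanced at the looks, up to 12.5% when slopes do not vary between people. This should be fixed: the effect is conditional, but the repair costs very little.

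**What to change.** **Preferred.** In Sample Size and Power, replace the undefined criterion with two-sided p<0.001 at any year 1 or year 2 efficacy look, on change in appendicular lean mass only, since that outcome sized the trial. State that the final lean mass test uses p<0.048. In Statistical Analyses, state that the same pre-specified model is used at each look and at the end. The 5% bound needs each test to keep its nominal size, and the section now chooses the time function by best fit and selects covariates from the data. Amend the last sentence of Criteria for Discontinuation to refer to this boundary.

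If the look times are fixed in advance, a final p<0.0488 gives 4.9% to 5.0% over the fractions examined. O'Brien-Fleming-type spending with 0.025 per tail is a reasonable alternative. At about 107.4 to 108.8 completers, it marginally exceeds the 108 expected at 10% dropout only in the late-look case.

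**Alternative.** If the sponsor wants no efficacy interim, say so in Sample Size and Power. Then amend both the committee's efficacy-assessment text and the stopping-rules sentence to agree. This changes the remit of a committee supplied by VA CSR&D, so it is more than a wording edit.

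**Cost.** The preferred option needs about 107 completers against 106, with 108 to 111 expected, so the 120 randomized need not change. The investigators must commit to lean mass as the stopping outcome. An early efficacy stop becomes harder, or impossible under the alternative. Neither option settles multiplicity across the performance measures.

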We hypothesized that insulin sensitizer (metformin/thiazolidinediones) use would also be associated with attenuated loss in physical performance in older diabetic women. In the Study of Osteoporotic Fractures, a multicenter, longitudinal cohort study, 2826 women aged \geq 70 years had physical performance measures assessed between 1997-1998 and 4.9±0.6 years later. Least squares mean change in 6-meter walk speed was estimated in multivariate linear regression models for women with no diabetes (n=2711), diabetes mellitus with no insulinsensitizers (n=162) and diabetes mellitus with insulin-sensitizers (n=30). After accounting for baseline age, race, BMI, education, self-rated health, hypertension, walk speed, and use of estrogen and statins, the decline in walk speed was significantly greater in women with diabetes who were not using insulin-sensitizers (-0.18 m/s, 95% CI -0.21, -0.15) than in women with no diabetes (-0.12 m/s, 95% CI -0.12, -0.11); whereas the loss in gait speed for women with diabetes. These results were unchanged after excluding women using insulin. These findings also remained unchanged after excluding 2 women on thiazolidinediones, suggesting that metformin use in older diabetic women may attenuate the loss in walk speed (data not yet published).

Summary

The longitudinal data from MrOS and SOF have helped to establish that insulin-resistant, older adults experience a greater loss in lean mass and physical performance. However, older adults with diabetes who were treated with metformin had a significant attenuation in the loss of lean mass and walk speed. These preliminary data provide the rationale for determining whether metformin can be used to prevent the loss of muscle mass and function. Although these observational results are compelling, validation with a randomized controlled trial is essential. Furthermore, a carefully performed trial will provide critical data about the mechanistic effects of metformin on muscle.

Research Design and Methods

Subjects and Experimental Design:

Overview

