The payments are reasonable and commensurate with the expected contributions of the subject. Each annual study visit is 2-3 hours. Baseline and annual visits include a fasting blood draw, height, weight, blood pressure, questionnaires, performance tests, and DXA. The procedures at every 6 month study visits (in between annual visits) are only fasting labs and questionnaires for all participants. For the muscle biopsy substudy, there will be a separate 1-2 hour visit at baseline and an additional 1 hour added to the 6 month visit.

Payments are fair and appropriate and do not constitute (or appear to constitute) undue pressure or influence on, or coercion of, the prospective research subjects to volunteer for or continue participation in the research study.

Statistical considerations

Sample Size and Power

Based on prior observational findings, there was a significant difference (2.2%, p< 0.01) in the percentage change in appendicular lean mass over 3.5 years between metformin-treated and untreated men. The sample size required for 80% Power to detect this difference and reject the null with SD=4% and α =0.05 for an unpaired, 2-sided t-test is 106 study participants (53 in each group). We plan to enroll 300 participants and, of those, randomize 120 (60 in each group) to allow for potential drop outs due to noncompliance and other reasons (7.5-10%). While 8-11% of participants may

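### The primary mixed model takes baseline as an outcome without stating a common baseline mean or baseline adjustment; for gait speed this could forgo about 2 to 11 points of power, and what the SD of 0.19 measures is not stated

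*Combined protocol and SAP*

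**What the plan says.** The Statistical Analyses section plans a longitudinal mixed model for each primary measure: "Four measures of muscle mass and performance (baseline, year 1, 2 and 3) are the outcomes in separate models". Time starts as linear and other shapes may replace it. Treatment enters as follows: "In the best fitting model, an interaction between time and group (metformin vs. placebo) will be included in the model". The text neither includes nor excludes a group main effect, so it does not settle whether the arms have separate baseline means.

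Covariates are governed by a confounding rule. The plan will "include them in multivariable models if they are significantly associated with our exposure and outcome and modify the effect size by >10" per cent. The candidates listed are demographics, activity, diet, lifestyle, medical history and medication. The baseline value of the outcome is not among them.

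The Study design section places the Baseline visit before randomization.

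Under Sample Size and Power, gait speed is the only performance measure with a power figure: "The sample size of 60 participants per group will have 73% Power to detect a 0.09 m/s difference in gait speed". The SD is 0.19, attributed to preliminary data in older women. The section does not say whether it is the SD of raw change or a residual SD after adjustment. The preliminary analysis of walk speed in women reports its estimates as follows: "After accounting for baseline age, race, BMI, education, self-rated health, hypertension, walk speed, and use of estrogen and statins".

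**The concern.** Because baseline is measured before randomization, the true baseline means of the arms are equal. A model with a separate baseline mean for each arm spends information on a difference known to be zero. Its treatment effect is then a contrast of raw changes, in which chance baseline imbalance remains. Constraining the baseline means to be equal, or adjusting for baseline, removes that noise at no cost.

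The confounding rule does not secure the gain. Baseline is not listed, and even if it were considered it would enter only after a significant chance imbalance between arms.

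Gait speed has the most to gain. Its stated power is already below 80%, and timed performance tests plausibly vary enough between visits for baseline adjustment to matter. There is also a question of match: if 0.19 came from a model that already adjusted for baseline walk speed, the 73% would belong to an adjusted analysis, and the plan does not state one.

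**Working it through.** **Inputs from the documents.** Gait speed: difference 0.09 m/s, SD 0.19, alpha 0.05, 60 per group (53 as the alternative size). Lean mass: 2.2% difference, SD 4%, 53 per group, unpaired two-sided t-test. The two-sided test is assumed for gait speed too.

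**Assumptions.** The correlation ρ between baseline and year 3 is not given; it is taken as 0.5 to 0.9. Variances are equal across visits and data are complete.

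**1. The plan's figure.** SE = 0.19 × √(2/60) = 0.0347, and 0.09/0.0347 = 2.594. Normal approximation: Φ(2.594 − 1.960) = 73.7%. Noncentral t: 73.0%. The stated 73% reproduces. At 53 per group the t-test gives 67.6%.

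**2. Why baseline matters.** With visit variance σ², raw change has variance 2σ²(1 − ρ). After adjustment for baseline the residual variance is σ²(1 − ρ²). The ratio is (1 + ρ)/2: 0.75, 0.85, 0.90 and 0.95 at ρ = 0.5, 0.7, 0.8 and 0.9.

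**3. The four-visit linear model, with 0.19 as the SD of raw change.** Set 2σ²(1 − ρ) = 0.19². By generalized least squares, the variance of the 3-year effect is 9 × Var(group-by-time slope), and power = Φ(0.09/SE − 1.960). Separate means: intercept, time, group, group-by-time. Common mean: the same without the group term. Two correlation structures are shown: compound symmetry (CS), and autoregressive (AR) scaled so that the baseline-to-year-3 correlation is ρ.

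| ρ | CS: separate → common | AR: separate → common |
|---|---|---|
| 0.5 | 78.1% → 89.1% | 73.7% → 85.1% |
| 0.7 | 78.1% → 84.2% | 73.7% → 80.4% |
| 0.8 | 78.1% → 82.0% | 73.7% → 78.1% |
| 0.9 | 78.1% → 80.0% | 73.7% → 75.9% |

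The gain runs from about 11 points at ρ = 0.5 to about 2 at 0.9.

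**4. The same model, with 0.19 as a baseline-adjusted SD.** Set σ²(1 − ρ²) = 0.19², so the SD of raw change is 0.19 × √(2/(1 + ρ)): 0.219, 0.212, 0.206 and 0.200 at ρ = 0.5, 0.6, 0.7 and 0.8. Power with separate means:

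| ρ | CS | AR |
|---|---|---|
| 0.5 | 65.9% | 61.3% |
| 0.6 | 68.7% | 64.1% |
| 0.7 | 71.3% | 66.7% |
| 0.8 | 73.7% | 69.2% |

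Steps 3 and 4 are alternatives. Their differences do not add.

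**5. What 0.19 might be.** For the 162 women with diabetes not on insulin-sensitizers, the adjusted change is −0.18 m/s (95% CI −0.21 to −0.15). The half-width of 0.03 implies SD = 0.03/1.96 × √162 = 0.195. Rounding of the limits allows half-widths of 0.025 to 0.035, so 0.162 to 0.227.

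**6. Lean mass.** The t-test at 53 per group gives 80.1%, as planned. Multiplying the SD by √((1 + ρ)/2) gives 82.1% at ρ = 0.9 and 81.1% at ρ = 0.95. A correlation this high is an assumption, but a plausible one for DXA lean mass.

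**The case against.** A reader might infer that the plan rejects baseline adjustment and so loses power. The text does not support that. It is silent on the group main effect, and a model with time and group-by-time but no group term already has a common baseline mean and loses nothing. What stands is that the text permits either model, and that conventional coding alongside an interaction would include the group term.

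A reader might also infer that the 73% is wrong. If 0.19 is the SD of raw change, 73% is correct for a simple comparison of changes and slightly conservative for the four-visit model. The link to a baseline-adjusted SD rests on one confidence interval rounded to two decimals. The three group sizes in that analysis sum to 2711 + 162 + 30 = 2903, against 2826 women stated, so 162 is not a secure denominator. The model adjusted for much besides walk speed and covered 4.9 years rather than 3. The match between 0.195 and 0.19 therefore justifies asking what the SD measures and shows no more than that.

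On importance, the time-by-group test is valid under randomization either way. The study was sized on lean mass, where little is at stake. Taking baseline as an outcome is a recognized approach that retains participants with missing follow-up. All of this stands and limits the weight of the point. It is not a reason to leave the model open, because the common-mean version keeps the same participants.

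**Conclusion.** The point holds as a free improvement in precision together with a request to define the SD. It is not a finding of bias, nor of an error in the stated power.

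If the arms are given separate baseline means, the four-visit model for gait speed forgoes about 11 points of power at correlation 0.5, 6 to 7 at 0.7, about 4 at 0.8 and about 2 at 0.9, taking 0.19 as the SD of raw change. These sizes rest on correlations that the documents do not give. If the group main effect is omitted, the loss is nil.

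Only if 0.19 is a baseline-adjusted SD could power fall below the stated 73%. Even then the shortfall depends on the correlation structure: at correlation 0.8 it disappears under compound symmetry but not under the autoregressive form.

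**What to change.** In Statistical Analyses, state for lean mass and each performance measure that the primary longitudinal model constrains the two groups to a common baseline mean, with no group difference at time 0, whatever form of time is chosen. Alternatively, model years 1 to 3 with the baseline value of the same measure as a prespecified covariate, outside the >10% confounder rule. In that version the treatment effect should be the adjusted group difference at year 3, since a time-by-group term over years 1 to 3 alone would miss any difference already present at year 1.

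In Sample Size and Power, say whether 0.19 is a raw-change or a baseline-adjusted SD, and restate the gait-speed power for the model that will be fitted, with the assumed correlation.

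The cost is wording and one recalculation, with no new participants, visits or measurements. The common-mean version keeps everyone with any measurement. The covariate version drops anyone without a baseline value, which should be almost nobody, and anyone with no follow-up value.
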